• Aim 3: Explore family caregiver and clinician RCT experiences to characterize how these participants may have been impacted by intervention components in a variety of implementation contexts, with a goal of understanding intervention mechanisms and barriers to future implementation and dissemination. Approach and goal: Using a mixed methods approach, we will integrate findings from both qualitative analysis of semi-structured interviews via telephone with family caregivers and clinicians as well as quantitative family caregiver, patient, and care process outcomes. This will provide insight into mechanisms of action and highlight methods for future intervention optimization through enhanced personalization, replicability, and scalability—all factors that are critical to successful implementation and dissemination of the intervention.

Primary and Secondary Outcomes

All outcomes have been piloted by the Duke University study team and chosen based on the conceptual model, expert recommendations, and psychometrics (Table 1).²⁻⁴ Response burden will be minimized with short instruments and online data entry via ePRO.⁵ Pilot testing confirmed completion in 15-20 minutes and demonstrated that all outcomes were responsive at levels of clinical significance.¹ Data will be collected at pre-randomization baseline (T1 Data Collection) as well as 4 days (T2 Data Collection), 8 days (T3 Data Collection), and 3 months (T4 Data Collection) post-randomization.

Primary Outcomes

For Aim 1, usability will be assessed with the SUS ⁶ and analysis of semi-structured interview transcriptions, while acceptability will be measured with the Client Satisfaction Questionnaire (CSQ-8).⁷

For Aim 2, the primary RCT outcome will be unmet palliative care needs at T3 (8 days post-randomization) as reported by family caregivers using the Needs; Existential concerns; Symptoms; and Therapeutic interaction (NEST) scale.^{1,8,9} The NEST, which assesses palliative care needs among both critically ill older adult patients and their family caregivers (and is completed by family caregivers), is the primary trial outcome and T3 is the primary timing of its measurement.⁹ The NEST's 13 items (score range 0-130) sample each of the National Consensus Project's eight domains of palliative care quality.¹⁰ The main patient-level outcome will be the receipt of goal concordant care at T2.^{11,12}

Secondary Outcomes

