Randomization will be stratified by three variables:

Protocol Version: 5.1 Dated: 13 June 2022 Page 8 of 42

- Department location at the time of ICU admission and informed consent (i.e., Medical versus Surgical)
- Palliative Care Trigger type (i.e., Acute versus Chronic; see Appendix 2)
- Baseline NEST score (i.e., ≥25 vs. <25 but ≥10)

All family members, regardless of their randomization arm will be asked to complete a total of four surveys, as listed below (see Appendix 3 for survey timeline):

- T1: to be completed within 72 hours of informed consent; study day 1
- T2: to be completed on study day 4
- T3: to be completed on study day 8
- T4: to be completed on study day 90

Surveys are completed remotely and electronically via the web application by the enrolled family member. Reminders are automatically provided by the PCplanner platform to the family members via email and/or text alerts to complete the surveys (Appendix 4).

Patients enrolled into this study, at the consent of their legally authorized representative (LAR), will passively participate in the study. Passive participation includes allowing the study team to access and abstract relevant clinical data from the patient's EMR. The clinical data abstracted for the purposes of this research project will be housed in the secure, EDC (REDCap).

Clinicians, whether ICU attending or Palliative Care, will be asked to complete a baseline survey at the time in which informed consent is obtained. The baseline survey will collect relevant information from the clinician, such as sociodemographic and professional information, as well a contact information (e.g., email address and cell phone number). Clinicians, who are assigned to an intervention family, will receive automatic text and/or email alerts via the web application informing them of the completed survey(s), reported needs, and the need to complete a family meeting.

Aim 3

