Analyses similar to those conducted for the NEST (primary outcome analyses) above will be performed for the secondary family caregiver hypotheses involving PHQ-9, GAD-7, and PTSS scores at T3 and T4. While family caregivers will be interviewed at T4 regardless of patient survival, patient death could complicate the analyses in two key ways: (1) Presence of missing data due to family loss to follow up (i.e., non-random missing data) and (2) differences in family caregiver distress by patient survival status (i.e., heterogeneous effect). 35 To address the impact of patient death on outcomes, after first exploring reasons for and predictors of dropout, we will conduct a 2-step supplemental analysis. In Step 1, missing T4 data due to loss to follow up among family caregivers of survivors will be multiply imputed via SAS PROC MI. In Step 2, we will account for T4 outcomes that are missing due to death via composite endpoint and principal stratification methods to estimate the causal effects of the intervention in the presence of these unidentified outcomes and complicated missing data patterns. 36,37 For the key patient outcome, receipt of goal concordant care, we will use logistic regression models adjusting for the stratification variables, to examine if rates at T3 differ by treatment group. The key healthcare systems outcome, post-randomization hospital length of stay (LOS), provides a unique challenge due to the high expected mortality rate (40-50%). In addition to descriptive analyses, steps to examine treatment group LOS differences will include: (1) a proportional hazards model with death treated as a censoring event; (2) a chi-square test of mortality rate differences; and (3) a Brunner-Manzel rank test for the composite death-LOS outcome. This last step implements a recently developed methodology of a composite outcome that incorporates a numerical value for death (i.e., coded as the worst possible outcome or the longest possible stay) in the observed LOS distribution. 38,39

Aim 3

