Transcribed interviews will be analyzed using a content analysis technique that combines *structural* (e.g., intervention component, palliative care process barriers) and *magnitude coding* (e.g., theme intensity) with *inductive coding* (e.g., variations in outcomes not captured by instruments).⁴⁰ The study team will separately code 10 interviews, discuss the generated codes, and create an initial code book by consensus. The code book will then be used by the study team for the next 10 transcribed interviews (with the PI coding each 5th interview). The final code book will be organized into categories used to generate themes of mechanistic and process elements. Narrative case summaries will be constructed and matrixed by patient case using *qualitative* analytic themes and *quantitative* data (e.g., triggers, needs, psychological distress, app use analytics). Across-case comparisons will be made using meta-matrices to search for patterns in intervention mechanisms of action common across theoretically- and empirically-derived categories of cases.⁴¹ Next, *process tracing* will be used to

Protocol Version: 5.1 Dated: 13 June 2022 Page **15** of **42**

explore how particular outcomes (e.g., needs, distress, goal concordance) may have been related to intervention components and their effect on process barriers in our conceptual model. 42,43

Sample Size and Power

Calculations were conducted via the mixed models with the differences in slopes option in PASS 2020 (Kayesville, UT). With a total of 130 participants at 8 days (n=65 per treatment arm), we will have 80% power to detect a differential NEST improvement between treatment groups of 8.80 units at 8 days (SD=21.1, ρ =0.64 between baseline and 8 days based on pilot data and an additional ongoing trial [NCT03506438]). To account for 10% dropout by 8 days, we plan to consent and randomize 150 participants (n=75 per treatment arm). This sample size will also provide a power of 80% (Type-I error of 5%, dropout rates as noted above) to detect a 2.33-unit PHQ-9 change (SD=5.3, ρ =0.6) at 8 days—far smaller even that it's 5.0-unit MCID. These estimates are based on our pilot work as well as an ongoing RCT (NCT03506438) we are conducting that uses the NEST

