Appendix 5: Data Collection and Timing

A. Clinical / patient information Baseline General information Comorbidities Diagnoses APACHE II illness severity CPR information / baseline ICU type & admission source Across entire hospitalization CPR information / changes Palliative care consults Procedures and therapies Dates (mechanical ventilation, hospital, ICU)	T1 Baseline x (x)	T2 4 days post- randomization	T3 8 days post- randomization	T4 3 months post- randomization - (x)
General information Comorbidities Diagnoses APACHE II illness severity CPR information / baseline ICU type & admission source Across entire hospitalization CPR information / changes Palliative care consults Procedures and therapies		-		- - (x)
CPR information / changes Palliative care consults Procedures and therapies	(x) -	-	-	- (x)
Dates (mechanical ventilation, nospital, 100)	-	-	-	(x)
3 months 3 month status				(^)
Patient & family member information				
Contact info Gender DOB, race / ethnicity, gender, marital status, children Employment Relation to patient Social support Financial distress	х	-	-	-
NEST	Х	Х	Х	-
Goal concordant care	X	x	X	-
Quality of communication	Х	х	Х	-
Patient-Perceived Patient-Centeredness (PPPC) scale	-	-	X	-
PHQ-9	X	-	X	Х
GAD-7	Х	-	X	Х
PTSS	X	-	Х	Х
Relationship with physician	X	Х	Х	-
Physician discussed needs	Х	Х	Х	-
Readmitted?	-	-	-	Х
Clinician information				
Gender Age Race / ethnicity Rank Service	Study initiation	-	-	-
Physician responses				
I did family meeting	-	Х	Х	-

CPR: cardiopulmonary resuscitation; GAD-7: generalized anxiety disorder 7-item instrument; ICU: intensive care unit; NEST: Needs; Existential concerns; Symptoms; and Therapeutic interaction scale; PHQ-9: patient health questionnaire 9-item depression instrument; PTSS: post-traumatic stress scale

Protocol Version: 5.1 Dated: 13 June 2022 Page 40 of 42

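### The goal-concordant-care model does not name the T1 value of the same measure as a covariate, although that value is collected before randomization; the test stays valid but is probably less precise than it could be

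*Combined protocol and SAP*

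**What the plan says.** All references are to the combined protocol and SAP.

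- **Model.** Section 8, Aim 2, covers the key patient outcome in one sentence: "we will use logistic regression models adjusting for the stratification variables, to examine if rates at T3 differ by treatment group". No other covariate is named.
- **Stratification variables.** Section 3, Study Overview, Aim 2: "Randomization will be stratified by three variables". They are department (medical or surgical), palliative care trigger type (acute or chronic) and baseline NEST (25 or more, or 10 to below 25). Baseline concordance is not one of them.
- **Data collected.** The row "Goal concordant care" in Appendix 5 is marked at T1, T2 and T3, but not at T4. Section 3 defines T1 as the baseline before randomization, and Section 5 has randomization follow completion of T1.
- **Status and visit.** Section 3, Primary Outcomes: "The main patient-level outcome will be the receipt of goal concordant care at T2". Section 8 tests T3.
- **Power.** Section 8 gives power for NEST and PHQ-9 only.

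**The concern.** A subject's own baseline value is often among the best available predictors of the later value. Here it is collected in the survey that precedes randomization, so using it needs no new data. The plan already draws on baseline for its other caregiver-reported measures: NEST is modelled as change over time, the distress scales get similar analyses, and the power statement relies on baseline correlations of 0.64 and 0.6. Goal-concordant care is the exception, and no reason is given.

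What is at stake is precision on the outcome that the protocol calls its main patient-level outcome, with a binary endpoint and about 65 per arm. If T1 concordance is added only after the data have been seen by arm, the adjustment becomes post hoc.

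**Working it through.** **1. The plan's own figure.** Section 8 assumes 65 evaluable caregivers in each arm and states "we will have 80% power to detect a differential NEST improvement between treatment groups of 8.80 units at 8 days". The inputs to that calculation are given as "SD=21.1, ρ =0.64 between baseline and 8 days". Using a two-sided 5% test (the plan gives 5% without sidedness):

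- Change-score SD = 21.1 × √(2 × (1 − 0.64)) = 17.90. Power for 8.80 with 65 per arm is 80.0%, as stated.
- Ignoring baseline (SD 21.1), power is 66%.
- Baseline as a covariate, SD = 21.1 × √(1 − 0.64²) = 16.21, power is 87%.
- PHQ-9: SD = 5.3 × √(2 × (1 − 0.6)) = 4.74. Power for 2.33 is 80.0%, as stated.

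The plan's power for these two outcomes therefore depends on using baseline. There is no corresponding figure for goal-concordant care to reproduce.

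**2. Assumptions for goal-concordant care.** None of these values is in the documents: control rate 30% to 60%, difference 15 to 25 points, T1-T3 phi 0.2 to 0.7. The 65 per arm is borrowed from the NEST calculation.

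**3. Approximation.** If T1 removes a share phi² of the outcome variance, the standardized effect is divided by √(1 − phi²):

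new power = Φ[(z(starting power) + 1.96) / √(1 − phi²) − 1.96]

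Example: starting power 70%, phi 0.6. (0.524 + 1.96) / 0.8 = 3.105; 3.105 − 1.96 = 1.145; Φ = 87.4%, a gain of 17.4 points.

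| phi | start 60% | start 70% | start 80% | start 90% |
|---|---|---|---|---|
| 0.2 | 1.8 | 1.8 | 1.6 | 1.1 |
| 0.3 | 4.1 | 4.0 | 3.6 | 2.5 |
| 0.4 | 7.5 | 7.4 | 6.4 | 4.3 |
| 0.5 | 12.4 | 11.8 | 9.9 | 6.3 |
| 0.6 | 19.0 | 17.4 | 13.8 | 8.2 |
| 0.7 | 27.3 | 23.6 | 17.5 | 9.5 |

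**4. Simulation.** Settings: 65 per arm, 3,000 trials per cell, Wald test from logistic regression on arm and three binary stratification factors, with and without binary T1 concordance. The T1 rate equals the control rate, and the strata explain 4% of the latent variance at each visit. Gains in power points:

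| Rates | Two-proportion power | phi ≈ 0.2 | ≈ 0.33 | ≈ 0.44 | ≈ 0.59 | ≈ 0.7 |
|---|---|---|---|---|---|---|
| 50% v 65% | 40.8% | 1.1 | 2.2 | 7.0 | 14.8 | 21.7 |
| 30% v 50% | 64.6% | 1.0 | 3.9 | 7.5 | 13.7 | 20.5 |
| 50% v 70% | 64.6% | 1.1 | 4.6 | 7.7 | 14.2 | 21.8 |
| 60% v 80% | 70.6% | 0.8 | 3.7 | 6.2 | 13.7 | 17.8 |
| 40% v 65% | 82.2% | 0.6 | 4.2 | 5.6 | 10.8 | 12.7 |
| 50% v 75% | 84.6% | 0.2 | 2.5 | 6.0 | 8.5 | 11.8 |

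Each simulated power has a standard error of up to √(0.25 / 3,000) = 0.9 points, so differences of about a point between cells are noise. At high phi the simulation gives smaller gains than the approximation, so the simulated ranges are used; at phi 0.2 the range of 0-2 covers both.

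**5. Validity.** In a smaller simulation (1,500 trials per scenario), type I error stayed between 4.5% and 5.5%.

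**The case against.** The case against giving this much weight is substantial.

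- **No stated figure is wrong.** The primary outcome is NEST at T3, whose longitudinal model uses the baseline value. No power is claimed for goal-concordant care, and adjusting for the stratification variables gives a valid test. This stands: the point is about efficiency. A reader might infer that an uncorrected chance imbalance at T1 biases the result. It does not, because randomization makes such imbalance part of the sampling error that the test already allows for.
- **The size is unknown.** A reader might take a middle band such as 3 to 17 points as the loss. That band corresponds to an assumed phi of about 0.3 to 0.6 with starting power of about 70% to 80%, and nothing in the documents fixes either. The upper end is also demanding. With 50% concordant at T1 and 70% at T3, the largest possible phi is (0.50 − 0.35) / √(0.25 × 0.21) = 0.65. A phi of 0.60 requires 97.5% of those concordant at T1 to remain so. This stands, and is why only a range by phi is given.
- **The sentence does not exclude other covariates.** True, but it names a specific set, and an unnamed covariate is not prespecified.
- **Baseline NEST band may carry some of the T1 information.** It may. A reader might infer that no stratification factor is a proxy for baseline concordance; the documents neither show nor rule that out. They show only that none of the three measures it directly.
- **A repeated-measures model is not an obvious improvement.** This stands. Section 8 expects 40-50% mortality, such a model would need a rule for concordance after death, and it was not simulated here.

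**Conclusion.** The point holds as an inexpensive gain in precision on the outcome called the main patient-level outcome. The planned model names only the stratification variables, and the T1 value of the same measure is collected before randomization and left out. The planned test remains valid.

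The gain ranges from almost nothing at phi 0.2 to 12-22 power points at about 0.7. As an illustration only, a latent correlation of 0.64 (the NEST value, not one for this outcome) corresponds to a phi of about 0.42-0.44 in the simulation, and so to 6-8 points. These figures rest on assumed rates, an assumed T1-T3 association and 65 evaluable per arm. The evaluable number for this outcome is not stated and could be lower if concordance is undefined after death.

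Separately, the documents disagree on the visit: T2 in Section 3, T3 in Section 8. The figures above use the 8-day sample size; the gain at T2 was not calculated.

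**What to change.** 1. In Section 8, Aim 2, prespecify T1 goal-concordant care as a covariate beside the three stratification variables, with a simple rule for a missing T1 response.
2. Report a standardized risk difference with a confidence interval, obtained by averaging the model's predicted probabilities under each arm. Adding a covariate changes what the conditional odds ratio estimates, so the target quantity should be stated.
3. Reconcile Section 3 (T2) and Section 8 (T3) on the outcome visit, and apply the T1 adjustment at whichever visit is kept.
4. Optional: a repeated-measures logistic model over T2 and T3, only with a stated rule for patients who die before the visit.

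Section 3 says that all outcomes were piloted, so the team may be able to estimate the T1-T3 association and replace the assumed range.

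Items 1 to 3 cost a few sentences in the analysis plan. They need no new data and no change in sample size, and should be settled before outcome data are seen by arm.

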As noted above, the DSMB will have the power to stop the trial at their discretion. The following is a possible stopping plan that could be adapted by the study DSMB for inclusion in the final DSMB Charter. Because this is an early phase trial, we will not have formal stopping rules based on efficacy or futility. Criteria for intervention discontinuation and stopping based on safety concerns will be determined in partnership with the study DSMB and codified in the DSMB charter before enrollment begins. We propose a strategy similar to that included in our past ICU-based RCTs that included family caregivers (e.g., R01 HL109823, PI: Cox). Three-month all-cause mortality will be the primary adverse event for the patients in study. We will examine the distribution of deaths by treatment arm three times during the trial: at 15, 25, and 50 deaths. At each of these interim looks, we will examine the distribution of deaths by study group and conducted either a non-parametric sign test or Wilcoxon signed-rank test to test the difference in median number of deaths between the arms. We will use Haybittle-Peto guidelines and stringently set the p-value at 0.001 to flag a significant difference between arms at each of these interim looks. If this difference is observed, this would then indicate a closer examination of related constructs, as well as proximate causes and circumstances surrounding death (e.g., timing and location of death, withdrawal of life support or not, comorbidities and illness severity, clinician expectations of survival). We will use the Patient-Centeredness of Care Scale to provide additional information on the alignment of patient treatment and values at the time of death. Although past end of life interventions have not increased mortality, it is possible that by better focusing decision makers' attention on patients' values, higher mortality could be observed in the intervention group by identifying patients for whom prolonged life support would be a state worse than death (Patrick DL, et al. Ann Int Med. 139:410-415, 2003; Holloway RG, et al. JAMA. 298:802-804, 2007). Yet if PCplanner—a non-directive intervention—led to more decisions to forego life support, this would be ethically permissible if the treatments received reflected patient-centered care as assessed by the PCCS (Institute of Medicine, 2001; Lin GA, et al. Arch Intern Med. 169:1551-1553, 2009; Holloway RG, et al. 2007). The primary adverse event for family caregivers will be symptoms of psychological distress as measured by the PHQ-9 and PTSS at T2 and T3. We propose to examine the distribution of scores by treatment arm three times during the trial: at 25, 75, and 100 caregivers. Using methods similar to those above, we could examine circumstances more closely as per DSMB guidelines.

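### The plan does not say how goal-concordant care is collected or scored when the patient dies between T1 and the survey, so its main patient-level comparison may be made in survivors only.

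*Combined protocol and SAP*

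**What the plan says.** Section 3 (Primary Outcomes) states: "The main patient-level outcome will be the receipt of goal concordant care at T2". Section 8, Aim 2, calls it the key patient outcome but places the test at a different survey: "we will use logistic regression models adjusting for the stratification variables, to examine if rates at T3 differ by treatment group". Appendix 5 marks the row "Goal concordant care" at T1, T2 and T3, and not at T4.

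Death is handled in Section 8 for other outcomes only:

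- For caregiver distress: "we will account for T4 outcomes that are missing due to death via composite endpoint and principal stratification methods".
- For length of stay, a composite in which death is "coded as the worst possible outcome or the longest possible stay".
- On continuing data collection: "While family caregivers will be interviewed at T4 regardless of patient survival". Nothing equivalent is written for T2 or T3.

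Section 10 (Patient Death While in Study) has study procedures halted at the patient's death, where applicable. Section 4 removes only patients who die before T1 is complete. Section 8 commits to intention to treat.

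**The concern.** A patient who dies between T1 and the survey stays in the randomised set but has no defined value on this outcome. Ordinary logistic regression omits records without an outcome, so unless the item is collected after a death, the comparison is restricted to survivors.

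That restriction may not be neutral here. Section 12 allows that mortality could be higher in the intervention arm because decision makers attend more closely to the patient's values, and says: "if PCplanner—a non-directive intervention—led to more decisions to forego life support, this would be ethically permissible", provided care was patient-centred. On that account, some early deaths could be instances of the concordance the intervention is meant to produce, and a survivors-only analysis would leave them out. An item never put to a bereaved caregiver cannot be recovered at the analysis stage, so the gap has to be closed during data collection.

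**Working it through.** **1. The plan's own figures.** No sample size, rate or power is stated for goal-concordant care. The NEST calculation in Section 8 reproduces: change-score SD = 21.1 × √(2(1 − 0.64)) = 17.90, which for 8.80 units at two-sided 5% gives 65 per arm and power 0.8001. It sets the trial size (75 randomised per arm) but says nothing about this outcome.

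**2. Can a rule be borrowed?** The T4 methods cannot apply, because goal concordance is not collected at T4. The length-of-stay composite ranks death worst, which does not carry over to an outcome where a death may be concordant. The patient-centredness scale that Section 12 uses at the time of death is described there for safety monitoring.

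**3. Is the item collected after a death?** Not stated. Section 10 points towards halting procedures. Appendix 3 marks End of Study beside Survival Status in the first family-meeting column as well as at day 90, which suggests that participation may end early after a death. Neither is conclusive.

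**4. Early deaths (assumed).** Section 8 gives 40–50% mortality in the length-of-stay discussion, with no day-4 or day-8 figure. Two readings bracket day 8:
- Constant hazard over 90 days: 1 − (1 − m)^(8/90) = 4.4% for m = 0.40 and 6.0% for m = 0.50.
- In-hospital mortality with an assumed median time to exit of 10–14 days: m(1 − 0.5^(8/median)) = 13–21%.

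I use 5–20%.

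**5. Effect of dropping deaths.** Assume 60% control concordance, a proportion d of control patients dead by the survey, and a proportion s of intervention patients moved from discordant survival to concordant death. The all-randomised difference is s. The survivors-only difference is 0.6(1 − d)/((1 − d) − s) − 0.6. SE = √(2 × 0.6 × 0.4/75) = 0.080, or 8.0 points.

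| s | d | All randomised | Survivors only | Gap | Gap/SE |
|---|---|---|---|---|---|
| 5 points | 5% | +5.0 | +3.3 | 1.7 | 0.21 |
| 5 points | 20% | +5.0 | +4.0 | 1.0 | 0.13 |
| 10 points | 5% | +10.0 | +7.1 | 2.9 | 0.37 |
| 10 points | 20% | +10.0 | +8.6 | 1.4 | 0.18 |

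**6. Wider range.** Let dC and dT be the proportions dead, and pC and pT the concordance among survivors. Three ways of treating the dead are excluded, all discordant and all concordant. The estimated differences are then related by:
- concordant minus discordant = dT − dC
- discordant minus excluded = dC·pC − dT·pT
- concordant minus excluded = dT(1 − pT) − dC(1 − pC)

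With 75 per arm, in units of the survivors-only SE (about 0.07–0.11):
- Equal deaths of 10–25% per arm: 0 with no effect, and 0.14–0.54 SE with a 10–20 point effect.
- Equal deaths of 45%, as an extreme: 0.48–0.83 SE with an effect.
- A 5-point death imbalance: largest movement 0.79 SE.
- A 10-point imbalance: largest movement 1.28 SE.

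One assumed case shows what can turn on the choice. With survivor concordance of 50% and 65%, and deaths of 15% control and 25% intervention, the difference is +0.150 (z 1.68) excluding deaths, +0.063 (z 0.77) scoring them discordant and +0.163 (z 2.13) scoring them concordant.

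A 10-point imbalance is not the typical case. At 20% deaths per arm the SE of the death difference is √(2 × 0.2 × 0.8/75) = 0.065, so an imbalance of 10 points or more arises by chance with probability of about 13%.

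**The case against.** The strongest reply is that the value may not be missing at all. The family member is the research subject and completes the surveys, alerts are timed from T1, and the halt in Section 10 is qualified. Appendix 5 schedules a patient-centredness scale at T3 only. If that is the scale Section 12 uses at the time of death, T3 must be answered for patients who have died. The item's wording and recall period are not in the documents, so it may already cover care up to death. This stands as far as it goes: the number of unscored patients is unknown, and a survivors-only analysis is a conditional consequence, not an established one. But the plan neither says that the item is asked after a death nor says how the answer would be scored.

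A reader might also infer that the choice moves the result by about one standard error in this trial. The documents do not support that. Movements of that size come from scoring the dead as not concordant, which the plan never proposes, or from a 10-point imbalance in early deaths, which is assumed. Section 12 itself notes that past end-of-life interventions have not raised mortality. Nor should 40–50% be read as the death rate by day 4 or day 8.

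**Conclusion.** The omission is real. The main patient-level outcome has neither a collection rule nor a scoring rule for deaths between T1 and the survey, although Section 8 provides for death in the T4 outcomes and in length of stay. The T2/T3 conflict adds to the problem, because it leaves open which deaths precede the survey.

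If the item lapses at death, the analysis conditions on survival after randomisation. The likely size of dropping the deaths is modest, about 0.13–0.37 SE, and rests on assumed concordance, assumed early mortality and the assumption that every extra death is concordant. The 0 to about 1.3 SE range describes the assumed grid and is not a bound.

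It would go too far to say that the arms are certainly not compared as randomised, or that each possible default is wrong, because both claims depend on item wording that the documents do not show. The outcome is not the trial's primary endpoint (caregiver NEST at T3) and has no stated power, so this is a worthwhile inexpensive improvement, not a threat to the trial.

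**What to change.** - Reconcile T2 in Section 3 with T3 in Section 8, so that one survey defines the outcome and the deaths that precede it.
- State in Section 8 and in Section 10 (Patient Death While in Study) that the caregiver's goal-concordance item is still offered at the scheduled survey after a patient death, with a lead-in that refers to care up to the death.
- Make the analysis of all randomised patients, using that answer for those who died, the main analysis of this outcome. Report survivors only as a sensitivity analysis. Fix both before unblinding.

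The cost is analysis-plan wording and one lead-in sentence to an item already in the T2 and T3 surveys, with no added patients or visits. The downside is that a bereaved caregiver's answer looks back over a few days, and some will decline, so the number of unanswered items after a death should be reported by arm.
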